### **9.1.3. Sensitivity Analyses of the Primary Analysis**

Three sensitivity analyses may be performed if the primary analysis is positive (statistically significant or strongly trending in favor of active treatment):

#### **9.1.3.1. Missing at Random Multiple Imputation**

Multiple imputation (MI) methodology will be utilized to impute complete datasets with three monthly observations for all patients in the mITT population. Monthly migraine counts will be computed as described in Section 9.1.1. This will yield 4 migraine count records per patient (baseline and 3 months follow-up). The missing values will be imputed for all patients/records using MI within each treatment group conditioned on each patients' non-missing data (including baseline), and the stratification factor. The Markov Chain Monte Carlo (MCMC) method will be used to produce 20 repeats of the data and seeds are given in [appendix 15.2](#). LS means and differences across the twenty MI reps will be combined using SAS procedure MIANALYZE ([Rubin, 1976](#)).

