#### **9.1.3.2. Multiple Imputation Tipping Point**

A tipping point analysis will be performed using the above MI datasets and applying an increasing delta (of higher migraine counts) to the active groups until statistical significance is no longer achieved. The delta will only be applied to imputed values; this will be done in 0.5 migraine day increments. This will only be performed if the primary analysis is significant. This will test the overall robustness of the primary analysis.

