## 15.2. Random Seeds

The following list of numbers will be used for random seeds where required for MI processes:

3954748

5375852

1235264

2575945

9454116

2624285

1783458

6572845

9458932

7855785

These will generally be used in order for the primary analysis, then secondary endpoints and sensitivity analyses. For cases where identical code may be applied to more than one outcome or a sensitivity analysis that uses a minor variation on the primary code, the second to last digit will be incremented by 1 to produce new seeds for the subsequent outcome/analysis. If a single dataset requires more than the 10 seeds above, additional seeds will be generated by incrementing the last digit by 1. All seeds used will be documented in the programming specifications and the programs themselves.

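### Twenty imputations are few for a tipping point read in 0.5-day steps: Monte Carlo error alone would often move the reported delta by one step, and at least 200 would largely cure this

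*SAP*

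**What the plan says.** SAP 9.1.3.1 imputes missing monthly migraine counts "within each treatment group conditioned on each patients' non-missing data (including baseline), and the stratification factor". On the number of imputations it says: "The Markov Chain Monte Carlo (MCMC) method will be used to produce 20 repeats of the data". The results are pooled with SAS MIANALYZE.

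SAP 9.1.3.2 builds on the same imputations: "A tipping point analysis will be performed using the above MI datasets", with a rising penalty on the active groups until significance is lost. On the grid it says: "The delta will only be applied to imputed values; this will be done in 0.5 migraine day increments". It also sets a condition: "This will only be performed if the primary analysis is significant".

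SAP Appendix 15.2 fixes the seeds in advance: "The following list of numbers will be used for random seeds where required for MI processes". It lists ten, gives their order of use and a rule for generating more.

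The visible text gives no reason for choosing 20, no target for Monte Carlo error, and no expected rate of missing Month 3 values in the mITT set. The nearest guide is the study schema (Protocol 3.1, Figure 1), which expects 265 of 300 randomized patients to complete treatment.

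**The concern.** The penalty reaches only the imputed values. When few values are imputed, one 0.5-day step barely moves the arm mean, so a small random error in the pooled treatment difference becomes a much larger error in delta. Every delta on the grid uses the same 20 datasets, so this error is shared along the whole grid and does not average out.

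What is at stake is the precision of one reported figure: the delta at which a significant result stops being significant. If another equally valid set of 20 imputations would often give a different grid value, reporting to the nearest 0.5 day claims more resolution than the analysis has.

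**Working it through.** **Inputs from the documents.** Protocol 10.2: effect 1.84 days, SD 3.95, about 100 per arm, two-sided alpha 0.05, and 0.025 for the first test. SAP 9.1.3: M = 20 imputations, step 0.5 day. Protocol Figure 1: 265 of 300 complete.

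**Assumptions not in the documents.** Share of Month 3 values imputed: f = 35/300 = 0.117, with 5 to 20% tested. Share of Month 3 variance explained by a patient's other data: R² = 0 to 0.7. A two-sample comparison stands in for the full model.

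**The plan's own figure first.** With 1.84 and 3.95, a normal approximation needs 97 per arm for 90% power; the exact t-test gives 90.05% at 98. At 100 per arm, t-test power is 90.6% at alpha 0.05 and 84.9% at alpha 0.025. The protocol's 100 per arm and approximately 85% are reproduced.

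**Monte Carlo error of the pooled difference.**
- Complete-data variance: W = 2 × 3.95² / 100 = 0.312.
- Total variance: T = W / (1 − f(1 − R²)). Between-imputation variance: B = f(1 − R²)T. Monte Carlo SD of the estimate: √(B/M).
- R² = 0: T = 0.353 (SE 0.594), B = 0.041, √(0.041/20) = 0.045 day, or 7.6% of the SE.
- R² = 0.7: T = 0.323 (SE 0.569), B = 0.0113, √(0.0113/20) = 0.024 day, or 4.2% of the SE.

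**The same error on the delta scale.**
- One step moves an active-arm mean by 0.5 × 0.117 = 0.058 day, so an error of 0.024 to 0.045 day is about 0.4 to 0.8 of a step.
- Dividing by f gives the error in delta: 0.024/0.117 = 0.20 day and 0.045/0.117 = 0.39 day.
- Over f from 5% to 20% the formula gives 0.16 to 0.57 day. The largest value is at 5% missing with R² = 0.

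**Simulation check.** 100 per arm, SD 3.95, effect 1.84, monotone dropout, regression imputation within arm, Rubin's rules; 30 seeds on each of 10 significant datasets. Between-month correlation 0.5, threshold 0.025:

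| Missing | M | SD of tipping delta (days) | Mean tipping delta (days) | Runs off the commonest grid value |
|---|---|---|---|---|
| 6% | 20 | 0.43 | 8.8 | 61% |
| 6% | 200 | 0.13 | 8.9 | 14% |
| 11.7% | 20 | 0.29 | 4.7 | 44% |
| 11.7% | 200 | 0.10 | 4.7 | 16% |
| 20% | 20 | 0.26 | 3.2 | 40% |
| 20% | 200 | 0.09 | 3.2 | 14% |

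At 11.7% missing and threshold 0.05, the SD at M = 20 is again 0.29, the mean tipping delta is 5.9 and 44% of runs are off the commonest value. At correlation 0.7 only the 6% case was simulated (SD 0.35 to 0.36 at M = 20).

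**Plausibility of the 44%.** A normal error of SD 0.29, with the noise-free value equally likely anywhere within a 0.5-day cell, changes the grid value 44% of the time, by two steps or more in about 2%. With SD 0.10 it does so 16% of the time.

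**Effect on the MAR p-value.** Take a noise-free p of exactly 0.025 (z = 2.241) and noise of 0.063 SE, within the 4 to 8% range. Then z = 2.241 ± 1.96 × 0.063 gives p from 0.018 to 0.034 with 20 imputations. With 200 the noise is 0.063/√10 = 0.020 SE, and p runs from 0.023 to 0.028.

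**The case against.** **The seeds are fixed.** A reader might infer that a favorable seed could be chosen afterwards. The documents do not support that: Appendix 15.2 lists the seeds, their order and a rule for more, so the run is reproducible. This part of the objection stands. Fixing the seed does not reduce the Monte Carlo error, however; the reported delta is still one draw.

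**The imputed treatment difference is precise enough.** A reader might also infer that the missing-at-random analysis itself carries noise comparable to 0.5 day. It does not. Its Monte Carlo SD is 0.024 to 0.045 day, less than a tenth of 0.5 day. It matters only if that p-value is borderline, and SAP 9.1.3 treats this as a sensitivity analysis that may be run, not as a decision test.

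**The robustness reading would seldom change.** In the simulations above, the noise is roughly 4 to 8% of the tipping delta. A tipping point is judged by whether the delta is clinically plausible, and the visible SAP sets no cut-off that one step would cross. To say that the result cannot be read as robust or fragile would go too far.

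**The inputs are proxies.** Completion is not the same as having a Month 3 value. SAP 4.2 excludes patients with no evaluable month, and SAP 9.1.1 keeps a month with at least 14 diary days. The simulation used monotone regression imputation and a simpler model than the planned MCMC and MMRM. These limits stand and are why a range is given.

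**Conclusion.** The point holds as a minor matter of precision, limited to the tipping delta. With 20 imputations and about 12% of Month 3 values imputed, the reported delta has a Monte Carlo SD of about 0.3 day (0.2 to 0.4 by the formula). That is the same order as the 0.5-day step, and roughly 40 to 45% of runs would give another grid value, usually the neighboring one. At about 6% missing the simulated share rises to between 55% and 62%, but the tipping delta itself is then about 9 to 11 days.

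The primary MMRM, the sample size and trial conduct are unaffected. The conclusion rests on the assumed missingness (5 to 20%), the assumed correlation between months, and a two-sample stand-in for the planned model. More imputations shrink the noise but do not abolish it: at 200, some 8 to 16% of runs at 11.7% missing still differ from the commonest value.

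**What to change.** In SAP 9.1.3.1, change the number of imputations from 20 to at least 200, and change the later sentence on pooling across the twenty repetitions to match. State in 9.1.3.2 that the tipping point uses this enlarged set. The SD of the tipping delta then falls to about 0.1 day (simulated 0.09 to 0.13; by the formula at 11.7% missing, 0.20/√10 = 0.06 to 0.39/√10 = 0.12), well below the 0.5-day step. Nothing here shows a need for more than that.

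The visible text of 9.1.3.3 does not give its number of imputations, so no change is proposed there beyond checking that it is consistent.

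The cost is two small edits to the SAP and a little computing time. The seed list in Appendix 15.2 can stay as it is.

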#### **9.1.3.2. Multiple Imputation Tipping Point**

A tipping point analysis will be performed using the above MI datasets and applying an increasing delta (of higher migraine counts) to the active groups until statistical significance is no longer achieved. The delta will only be applied to imputed values; this will be done in 0.5 migraine day increments. This will only be performed if the primary analysis is significant. This will test the overall robustness of the primary analysis.

#### **9.1.3.3. Missing Not at Random Multiple Imputation**

Finally, a missing-not-at-random multiple imputation approach will be utilized taking into account the reason for discontinuation.

Missing monthly migraine counts for participants in the mITT population will be imputed via multiple imputation (MI). 

#### **9.1.4. Secondary Analyses of the Primary Endpoint**

Two additional analyses of the number of headache days will be performed:

##### **9.1.4.1. Mean Change Over the Full 12 Week follow-up**

The mean change in the number of migraine headache days from the last 28 days of Baseline to average number per 28 days over the entire 12-week duration of Treatment Period will be compared among the treatment groups. This will utilize the same model and output as the primary analysis, but will report model contrasts averaging the three follow-up months. Least square means (LSMs), standard errors, and the LSM differences (each treatment vs placebo) will be reported for these averages.

##### **9.1.4.2. Patients Experiencing a $\geq 50\%$ Reduction in Migraine Headaches**

Finally, for each patient and month, patients will be flagged as responders if they experience a  $\geq 50\%$  reduction in the number of migraine headache days from the last 28 days of Baseline to the given month's 28-day normalized migraine headache days. The percent change from baseline will be calculated for each month as  $100 * [\text{monthly count} - \text{baseline count}] / [\text{baseline count}]$ . The number and percentage of patients achieving  $\geq 50\%$  improvement will be reported as well as 95% CIs for the percentages. Patients with missing data will be considered non-responders/ not achieving either improvement threshold. The difference in percentages in the active and placebo arms from the Cochran-Mantel-Haenszel (CMH) common risk difference estimator will be reported along with its 95% CI based on the Sato variance estimator. Pairwise p-values will compare each treatment arm to placebo based on a CMH stratified by preventive medication use. The primary time point of interest will be month 3, but each month will be summarized.

## 9.2. Secondary Endpoints

All secondary efficacy analyses will be based on the mITT population.

### 9.2.1. Key Secondary Endpoints

There will be six key secondary endpoints:

- Proportion of patients experiencing a  $\geq 50\%$  reduction in the number of migraine headache days from the last 28 days of Baseline to the last 28 days of treatment in each treatment group (described in Section 9.1.4.2 above).
- Mean change in the number of days using rescue medication (triptan, ergot derivative, or other migraine-specific acute medication) from the last 28 days of Baseline to the last 28 days of treatment.
- Proportion of patients with a Patient Global Impression of Change (PGIC) rating of 1, “very much improved”, or 2, “much improved”, at Week 12.
- Mean change in the number of moderate or severe headache days from the last 28 days of Baseline to the last 28 days of treatment. A moderate or severe headache day is defined as any calendar day wherein a patient records a headache or migraine of moderate or severe peak intensity in the e-diary.
- Mean change in the number of migraine headache days from the last 28 days of Baseline to average number per 28 days over the entire 12 week duration of Treatment Period (described in Section 9.1.4.1 above).
- Mean change from Baseline in the Migraine-Specific Quality of Life Questionnaire Role Function, Restrictive domain (MSQ v2.1) at Week 12.

#### 9.2.1.1. Rescue Medication Use

The Mean change in the number of days using rescue medication from the last 28 days of Baseline to the last 28 days of treatment will be compared among the treatment groups. A rescue medication use day is any calendar day (0:00 to 23:59) in which the patient records the use of a triptan, ergot derivative, or other migraine-specific abortive medication (see Appendix 15.5). Calculation and analysis of this will be identical to the primary with the substitution of days using rescue medication for migraine days. Least square means (LSMs), standard errors, and the LSM differences (each treatment vs placebo) will be reported for these averages. As with the primary endpoint, Kruskal-Wallis tests will be performed and reported.

#### 9.2.1.2. Patient Global Impression of Change

The number and percentage and 95% CIs for the percentages will be reported for patients with a PGIC rating of 1, “very much improved”, or 2, “much improved”, at Week 12 for each treatment group. Patients with missing data will be considered non-responders. The difference in percentages in the active and placebo arms will be reported along with its 95% CI (using the Sato estimator of variance). Pairwise p-values will compare each treatment arm to placebo based on a

CMH stratified by preventive medication use. The primary time point of interest will be Week 12, but each time point collected will be summarized.

#### **9.2.1.3. Mean Change in Moderate or Severe Headaches**

The mean change in the number of moderate or severe headache days from the last 28 days of Baseline to the last 28 days of treatment (i.e. month 3) will be compared among the treatment groups. A moderate or severe headache day is any calendar day (0:00 to 23:59) in which the patient records an attack of moderate or severe peak intensity in the e-diary. Calculation and analysis of this will be identical to the primary with the exception that only days with moderate or severe headache will be included in the tally. Least square means (LSMs), standard errors, and the LSM differences (each treatment vs placebo) will be reported for these averages. As with the primary endpoint, Kruskal-Wallis tests will be performed and reported.

#### **9.2.1.4. Mean Change in the Migraine-Specific Quality of Life Questionnaire (MSQ)**

For the MSQ v2.1, items are scored 1-6; the total and three sub-domains will be calculated and scaled such that the resulting values will be scaled 0-100, with higher scores indicating better quality of life. The Role Function, Restrictive domain will be a key secondary endpoint and the other items & total will be additional secondary endpoints.

The total MSQ will be calculated as the sum of the 14 individual questions, minus 14, then scaled by 100/70. Missing values will be imputed with the means of the non-missing values, as long as there are at least 7 non-missing values.

Role Function – Restrictive: Items 1-7 will be summed, then 7 subtracted from the value, and this scaled by 100/35. Missing values will be imputed with the means of the non-missing values, as long as there are at least 4 non-missing values. If there are less than 4 values, then the score will be set to missing.

Role Function – Preventative: Items 8-11 will be summed, then 4 subtracted from the value, and this scaled by 100/20. Missing values will be imputed with the means of the non-missing values, as long as there are at least 2 non-missing values. If there are less than 2 values, then the score will be set to missing.

Emotional Function: Items 12-14 will be summed, then 3 subtracted from the value, and this scaled by 100/15. Missing values will be imputed with the means of the non-missing values, as long as there is at least 1 non-missing value. If there are less than 2 values, then the score will be set to missing.

Summary statistics (mean, SD, median, minimum, maximum) will be reported for the change from the baseline in each MSQ v2.1 score to each visit and for each of the treatment groups. The change from baseline will be analyzed in an MMRM model with fixed effects of treatment, visit, baseline value, treatment by visit interaction, and stratification factor (preventive medication use); an unstructured covariance matrix will be used. LSMs, standard errors, and the LSM differences (each treatment vs placebo) with 95% CIs and p-values will be reported for each visit (with week 12 being of primary interest). Denominator degrees of freedom will use the Kenward Rogers approach. Should the model fail to converge, heterogeneous Toeplitz, heterogeneous first-order autoregressive, Toeplitz, first order autoregressive and compound symmetric will be

attempted in that order; in these cases, the sandwich estimator (Diggle and Kenward 1994) will be used to estimate the standard errors of the fixed effects parameters and the denominator degrees of freedom will utilize the DDFM=BETWITHIN option in SAS®.

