# 6.8.4 Migraine-Specific Quality of Life Questionnaire v2.1

At Visits 2, 3, 4, and 5, patients will be asked to complete the Migraine-Specific Quality of Life Questionnaire version 2.1 (MSQ). The MSQ has been shown to have good psychometric performance in measuring headache impact in migraine patients. The MSQ is a 14-item patient-reported outcome instrument that measures the impact of migraine across 3 essential aspects of a patient's health-related quality of life over the past 4 weeks: role function-restrictive, role function-preventive, and emotional function. Patients respond to items using a 6-point scale: "none of the time," "a little bit of the time," "some of the time," "a good bit of the time," "most of the time," and "all of the time," which are assigned scores of 1 to 6, respectively. Raw dimension scores are computed as a sum of responses and rescaled from a 0 to 100 such that higher scores indicate better quality of life.

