- Mean change from Baseline in the Migraine-Specific Quality of Life Questionnaire Role Function, Restrictive domain (MSQ v2.1) at Week 12.

The order of the other secondary analysis will be:

- Mean change from Baseline in the Migraine Disability Assessment (MIDAS) Test total score at Week 12.
- Mean change from Baseline in the Hospital Anxiety and Depression Scale (HADS) total score at Week 12.
- Mean change from Baseline in patient-rated Changes in Sexual Functioning Questionnaire Short-Form (CSFQ-14) total score in males and in females, analyzed separately, at Week 12.

The exploratory analyses will be:

- Proportion of patients experiencing a  $\geq 75\%$  reduction in the number of migraine headache days from the last 28 days of Baseline to the last 28 days of treatment in each treatment group.
- Proportion of patients with fewer than 14 headache days or fewer than 8 migraine headache days per 4 weeks over the 12-week period.
- Mean change from Baseline in number of headache free days from the last 28 days of Baseline to the last 28 days of treatment

Although all p-values will be non-significant following the first to fail to meet its alpha threshold, p-values will be reported for all the above endpoints; they will be noted as descriptive for those following the first non-significant p-value.

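### The SAP's MSQ formulas omit the reverse-coding step, so they score no migraine impact as 0 and maximal impact as 100, the opposite of the stated direction, on a key secondary endpoint.

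*SAP*

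**What the plan says.** Protocol 6.8.4 describes the MSQ v2.1 as a "14-item patient-reported outcome instrument that measures the impact of migraine across 3 essential aspects" of health-related quality of life. It lists six responses running from none of the time to all of the time, "which are assigned scores of 1 to 6, respectively. Raw dimension scores are computed as a sum of responses". The dimension scores are then "rescaled from a 0 to 100 such that higher scores indicate better quality of life".

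SAP 9.2.1.4 repeats the 1 to 6 item scoring and the intended direction: "the resulting values will be scaled 0-100, with higher scores indicating better quality of life". It then gives four formulas of one form: sum the items, subtract the number of items (the lowest possible sum), and multiply by a positive constant. For the Restrictive domain it reads "Items 1-7 will be summed, then 7 subtracted from the value, and this scaled by 100/35". The total uses 14 items and 100/70, the Preventative domain four items and 100/20, and the Emotional domain three items and 100/15.

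SAP 8.1.5 puts this measure last of the six key secondary endpoints in the alpha-controlled order: "Mean change from Baseline in the Migraine-Specific Quality of Life Questionnaire Role Function, Restrictive domain (MSQ v2.1) at Week 12". SAP section 8 defines change from baseline as the later value minus the baseline value.

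**The concern.** A formula that only subtracts a constant and multiplies by a positive number keeps the direction of the raw sum. Under the protocol's coding, a larger raw sum means that migraine interferes more often. The final score would therefore also rise with impact, which contradicts the direction stated in the same SAP section and in the protocol.

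The Restrictive domain carries a planned inferential claim for each dose. If the formula is programmed as written and the output is labelled higher = better, a real benefit of active drug appears as a negative LS-mean difference and reads as worsening. A real worsening appears as a positive difference and reads as benefit. SAP 8.1.5 describes the testing sequence through p-value thresholds alone, so no stated step would catch a wrong sign. The total and the other two domains, which are additional secondary endpoints, would be inverted in the same way.

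**Working it through.** **Inputs**

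- Item codes: 1 = none of the time, rising to 6 = all of the time (Protocol 6.8.4).
- What the items measure: the impact of migraine, so a higher code is worse (Protocol 6.8.4).
- Intended final scale: 0 to 100, higher = better (Protocol 6.8.4 and SAP 9.2.1.4).
- SAP formula for a scale of k items: (sum - k) x 100/(5k), with k = 7, 4, 3 and 14 (SAP 9.2.1.4).
- Change = post-baseline minus baseline (SAP section 8).

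**Step 1: range.** The item range is 6 - 1 = 5, so the raw range is 5k: 35, 20, 15 and 70. These match the SAP's divisors, and the 0 to 100 range is reproduced.

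**Step 2: direction.** If every Restrictive item takes the same value v, the sum is 7v. The SAP score is (7v - 7) x 100/35 = 20(v - 1). The reversed score is (42 - 7v) x 100/35 = 20(6 - v).

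| Every item at | Sum | SAP formula | With reversal |
|---|---|---|---|
| 1 (none of the time) | 7 | 0 | 100 |
| 2 | 14 | 20 | 80 |
| 3 | 21 | 40 | 60 |
| 4 | 28 | 60 | 40 |
| 5 | 35 | 80 | 20 |
| 6 (all of the time) | 42 | 100 | 0 |

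The other three formulas give the same two sequences, because k cancels: (kv - k) x 100/(5k) = 20(v - 1). The stated range is reproduced, but the stated direction is not.

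**Step 3: effect on a change score.**

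- Improvement from 4 to 3 on all seven items: the sum falls from 28 to 21. The SAP formula gives 60 to 40, a change of -20. With reversal it is 40 to 60, a change of +20.
- Improvement from 5 to 3 on all seven items: the sum falls from 35 to 21. The SAP formula gives 80 to 40, a change of -40. With reversal it is 20 to 60, a change of +40.

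**Step 4: effect on the model.** The two scores are related by reversed = 100 - SAP score. Every change from baseline is therefore multiplied by -1, and the baseline covariate is replaced by 100 minus itself. The MMRM in SAP 9.2.1.4 fits equally well either way. The LS-mean difference changes sign, while its absolute size, its standard error and the two-sided p-value stay the same.

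**Step 5: is a reversal stated elsewhere?** Protocol 6.8.4 forms the raw score as a plain sum of responses and leaves the direction to the rescaling. SAP 9.2.1.4 specifies that rescaling and does not reverse it. By contrast, Protocol 6.9.3 says which two CSFQ-14 items run the other way and gives their coding. For the MSQ, the only coding given is the unreversed one.

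**The case against.** The strongest reply is that the SAP states the right direction before it gives the formulas and does not itself say which response is scored 1. If its 1 to 6 scores were already recoded, the formulas would be correct, and a programmer who compared the output with the stated direction would notice the conflict. But nothing in the text supports that reading. The protocol's coding is the only one given, and it sums the responses directly. A correct result would depend on a step that neither document contains.

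Four further points limit the consequence:

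- The two-sided p-values do not change, so the alpha arithmetic and every other endpoint are untouched. This stands: the error concerns reported direction, not type I error.
- The domain comes last in the order. The primary and five key secondaries at two doses make 6 x 2 = 12 comparisons that must succeed first; otherwise the MSQ p-value is descriptive. This stands, but a descriptive result with the wrong sign still misleads.
- The documents do not reproduce the item wording. That none of the time means least impact is inferred from the protocol's description of the instrument. The inference is reasonable. If some items ran the other way, a reversal rule would still have to be stated.
- No derivation code is available, so the sign will be wrong only if the formula is programmed literally. This is true, and it is why the written specification needs correcting.

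**Conclusion.** The concern holds. Read with the only item coding that the documents give, all four MSQ formulas run opposite to the direction that the protocol and the SAP both state. The reversal is complete: 0 and 100 are exchanged at the extremes, and every change and treatment difference keeps its size but takes the wrong sign. A one-category improvement across the Restrictive domain becomes -20 in place of +20.

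The conclusion rests on two assumptions: that more frequent responses mean more migraine impact on these items, as the protocol's description implies, and that the formula is programmed as written. It must be fixed, because following the written specification of a key secondary endpoint yields the opposite of its stated meaning.

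**What to change.** In SAP 9.2.1.4, state that every item is recoded as 7 - x before summing and keep the existing formulas. Equivalently, replace them with:

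- Restrictive = (42 - sum of items 1 to 7) x 100/35
- Preventative = (24 - sum of items 8 to 11) x 100/20
- Emotional = (18 - sum of items 12 to 14) x 100/15
- Total = (84 - sum of all 14 items) x 100/70

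Replacing missing items by the mean of the answered ones gives the same score before or after recoding. If the answered Restrictive items have mean m, the completed raw sum is 7m and the recoded sum is 7(7 - m) = 49 - 7m. Subtracting 7 leaves 42 - 7m either way.

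Add a programming check that all-1 responses score 100 and all-6 responses score 0. If the derivation code already exists, run that check on it before any MSQ result is read.

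A separate point in the same section should be settled in the same edit. The Emotional Function missing-item rule contradicts itself: it allows imputation with one answered item, then sets the score to missing with fewer than two. This has no bearing on direction.

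The cost of the recoding is one sentence in the SAP and one line of derivation code. It needs no new data and does not affect the sample size or the testing order.
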